3.2 DISCUSSION OF TRIAL DESIGN, INCLUDING THE CHOICE OF CONTROL GROUP

The aim of this study is to evaluate the efficacy and safety of empagliflozin 10 mg and 25 mg in Japanese patients with T2DM whose glycaemic control is insufficient despite diet/exercise and treatment with insulin.

The design of this study is decided according to the draft version of the revised Japanese guideline 'Clinical Evaluation Guidelines for Antihyperglycemic Drugs' [[R15-2907](#)] in which 1-year long-term study is required for any antihyperglycemic investigational product when used as added-on therapy to existing antihyperglycemic drugs which are expected to be co-administered in clinical practice.

Patients who are pre-treated with insulin in combination with 1 OAD will undergo a 10-week wash-out period before a 2-week open-label placebo run-in period. Patients who are pre-treated with insulin alone will skip the wash-out period and proceed to the placebo run-in period.

The 10-week wash-out period will minimise the effect of pre-treated OAD on glycaemic control in patients treated with insulin in combination with the OAD prior to randomisation.

The 2-week open-label placebo run-in period is set to confirm whether the patients fulfil the entry criteria for the double-blind treatment period and to check medical compliance by mimicking the dosing in the double-blind treatment period.

A double-blind and double-dummy design is adopted in order to minimize bias to evaluate the efficacy and safety of two doses (i.e. 10 mg and 25 mg) of empagliflozin and in comparison with placebo, and the 52 weeks of treatment duration is planned in order to investigate the long term efficacy and safety of empagliflozin.

The 1-week follow-up period is considered to be sufficient, as previous studies with empagliflozin have shown that the pharmacodynamic effect of empagliflozin only extends to about 3 days after the last dose and half-life of empagliflozin in Japanese T2DM after 4 weeks of treatment was 12 to 18 hours.

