3.3.2 Inclusion criteria

1. Diagnosis of type 2 diabetes mellitus prior to informed consent. This diagnosis should be confirmed by clinical judgment and negative results of Anti-GAD antibody and Anti-IA-2 antibody at Visit 1 (screening).
2. Male and female patients on diet and exercise regimen who are pre-treated with any insulin therapy^{a)} alone^{c)} or in combination with 1 oral antidiabetic drug (OAD)^{b), c)} for at least 12 weeks prior to Visit 1 (screening).
 - a) Any kind of insulin therapy (Basal-Bolus therapy, Bolus insulin therapy, Premix insulin therapy and Basal insulin therapy) approved in Japan is allowed. The choices of insulin product, dosage and usage have to follow respective insulin product label in Japan at Visit 1 (screening).
 - b) Sulfonylurea is permitted as a pre-treatment drug only if the dose is not more than a half of daily maximum approved dose. Any other OADs except thiazolidinedione and SGLT-2 inhibitors are allowed at any dose within approved dose.
 - c) If patients are pre-treated by insulin with 1 OAD at Visit 1, the OAD should be stopped and washed-out for 10 weeks prior to Visit 4 (placebo run-in). For patients receiving insulin alone at Visit 1, no wash-out (of any drug) is necessary.

Insulin product and its usage must be unchanged at least from 12 weeks prior to Visit 1 (screening). Total prescribed dose must be ≥ 10 U/day, and it has to be within a defined area at least 12 weeks prior to Visit 5 (randomization) in patients who are pre-treated by insulin alone and from Visit 1 in patients who are pre-treated by insulin in combination with 1 OAD.

The defined area is as follows,

In case of the insulin dose at 12 weeks prior to Visit 5 in patients who are pre-treated with insulin therapy alone (at Visit 1 in patients who are pre-treated with insulin in combination with 1 OAD) is

- ≥ 20 U/day: Within $+\/- 10\%$ change from the dose at Visit 5 is allowed.
- ≥ 10 U/day and < 20 U/day: Within $+\/- 2$ U change from the dose at Visit 5 is allowed. (insulin dose < 10 U is not allowed prior to and at Visit 5)

3. Fasting C-peptide: > 0.5 ng/mL at Visit 4 in patients who are pre-treated with insulin alone (at Visit 2 in patients who are pre-treated with insulin in combination with 1 OAD)
4. Patients who are treated with insulin alone:
 - HbA_{1c} at Visit 1: $\geq 7.5\%$ and $\leq 10.0\%$ (HbA_{1c} at Visit 4 is to be skipped)
5. Patients who are treated with insulin with 1 OAD:

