 - HbA_{1c} at Visit 1: $\geq 7.0\%$ and $\leq 9.5\%$
 - HbA_{1c} at Visit 4: $\geq 7.5\%$ and $\leq 10.0\%$

Proprietary confidential information © 2016 Boehringer Ingelheim International GmbH or one or more of its affiliated companies

6. Age at informed consent: ≥ 20 years and <75
7. BMI (body mass index) at Visit 1: >22 and $\leq 40 \text{ kg/m}^2$
8. Signed and dated written informed consent by date of Visit 1 in accordance with Good Clinical Practice (GCP) and Japanese legislation

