7.6 RANDOMISATION

The trial will be performed as a double-blind design with respect to placebo and 2 active treatment groups of empagliflozin (10 mg and 25 mg). Patients who meet the inclusion criteria but not meet the exclusion criteria will be randomised in 1:1:1 ratio to each treatment group at Visit 5.

The randomisation will be stratified by the following factors:

- Baseline HbA_{1c} (at Visit 1 for insulin alone, Visit 4 for insulin with one OAD) (<8.5% or <69.4 mmol/mol, ≥8.5% or ≥69.4 mmol/mol)
- Baseline Renal function (at Visit 4) (eGFR <60 mL/min/1.73 m², eGFR ≥60 mL/min/1.73 m²)
- Type of insulin therapies (basal insulin therapy, other insulin therapy)

The randomisation of patients to the treatment groups will be performed via an IRT. BI will arrange for the randomisation as well as packaging and labelling of trial medication. The randomisation list will be generated using a validated system, which involves a pseudorandom number generator and a supplied seed number so that the resulting allocation of medication numbers to treatment is both reproducible and non-predictable. The access to the randomisation codes will be controlled and documented.

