## **6.2      IMPORTANT PROTOCOL VIOLATIONS**

Not all important protocol violations (IPV) will generate exclusion from the per protocol population. Violations that lead to exclusion from analysis populations are indicated as such in [Table 6.2.1](#)

The decision about which IPV could generate exclusion from analysis sets will be taken during the course of the study and finalised at the last blinded report planning meeting (BRPM).

Table 6.2: 1 Important Protocol Violations

Category / Code	Description		Comment/Example	Excluded from
A	Entrance Criteria Not Met			
A1	Target indication not met			
	A1.01	No type 2 diabetes	INC1 checked	PPS
	A1.02	Antidiabetic background therapy not as required	INC2 checked	PPS
A2	Inclusion criteria violated			
	A2.01	HbA 1c out of range	HbA 1c out of range for inclusion by more than 0.2% for insulin alone: [7.5%, 10%] at Visit 1 for insulin with 1 OAD: [7.0%, 9.5%] at Visit 1 [7.5%, 10%] at Visit 4	PPS
	A2.02	Age out of range	INC6 checked and calculated date checked	None
	A2.03	BMI out of range	INC7 checked	None
	A2.06	Fasting serum C-peptide levels out of range	INC3 checked	None
A3	Exclusion criteria violated			
	A3.01	Uncontrolled FPG level	EXC1 checked	None
	A3.02	Additional background therapy	EXC2 checked	PPS
	A3.03	Relevant concomitant diagnoses	EXC3, EXC7 checked	None
	A3.04	Bariatric or other relevant gastrointestinal surgery within the past two years	EXC6 checked.	PPS
	A3.05	Blood dyscrasias or any disorders causing hemolysis or unstable red blood cell	EXC8 checked	PPS
	A3.06	Indication of liver disease	EXC4 checkedParameters above 3 ULN at screening or during run-in period	None
	A3.07	Contraindication to any of the drugs in the study regimen	EXC9 checked	None
	A3.08	Treatment with protocol excluded anti-obesity drugs	EXC11 checked	PPS
	A3.09	Renal insufficiency or renal impairment (assessed by eGFR)	EXC5 checked: eGFR < 45mL/min/1.73m  during screening or run-in period	PPS
	A3.10	Treatment with protocol excluded systemic steroids or change in thyroid hormone dose	EXC12 checked	PPS
	A3.11	Intake of an investigational drug in another trial within 30 days prior to intake of study medication in this trial	EXC15 checked, review at MQRM/BRPM to determine efficacy impact (Medical judgement), depending on the type of drug given in the prior trial (only if investigational drug interferes with glucose metabolism).	PPS Final decision at the DBL meeting

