#### **7.4.1 Primary efficacy analysis**

The primary analysis is an analysis of covariance (ANCOVA) comparing the change from baseline in HbA1c after 16 weeks of treatment. All randomised treatment groups will be included in the same analysis. The statistical model will be:

Change from baseline in HbA1c after 16 weeks = overall mean + baseline HbA1c + treatment + baseline renal function + type of insulin therapies + random error

This model includes effects accounting for the following sources of variation: 'baseline HbA1c', 'baseline renal function', 'type of insulin therapies' and 'treatment'. 'Treatment', 'baseline renal function', and 'type of insulin therapies' are fixed classification effects and 'baseline HbA1c' is a linear covariate. Note that baseline renal function refers to the eGFR categorization ( $\geq 60$  mL/min/1.73 m^2,  $< 60$  mL/min/1.73 m^2). Such categorization is applicable to the analysis of other endpoints as well.

The random error is assumed to be normally distributed with mean 0 and unknown variance. The primary analysis will be performed on the FAS with treatment assignment as randomised.

A hierarchical testing sequence will be used as defined in the protocol.

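### Pre-treatment cohort (insulin alone, or insulin plus one washed-out OAD) is missing from the primary ANCOVA and the sensitivity MMRM: a small, cheap loss of precision

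*Protocol*

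**What the plan says.** **Two cohorts.** Protocol 3.3.2 admits patients on insulin alone or on insulin with one OAD. For the second group, "the OAD should be stopped and washed-out for 10 weeks prior to Visit 4 (placebo run-in"); the first group skips wash-out. The flow chart puts the start of wash-out at week -12, Visit 4 at week -2 and randomisation at Visit 5.

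**Entry HbA1c.** The violation table in SAP 6.2 restates the ranges: "for insulin alone: [7.5%, 10%] at Visit 1", and "for insulin with 1 OAD: [7.0%, 9.5%] at Visit 1 [7.5%, 10%] at Visit 4". The last qualifying range is therefore 7.5–10.0% in both cohorts, and OAD patients also pass a screen on treatment at Visit 1.

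**Purpose of wash-out.** Protocol 3.2: "The 10-week wash-out period will minimise the effect of pre-treated OAD on glycaemic control".

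**Randomisation.** Protocol 7.6 stratifies on HbA1c (below 8.5%, or 8.5% and above), eGFR (below 60, or 60 and above) and "Type of insulin therapies (basal insulin therapy, other insulin therapy"). Cohort enters only by deciding which visit supplies the HbA1c for the first factor.

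**Models.** SAP 7.4.1: "Treatment', 'baseline renal function', and 'type of insulin therapies' are fixed classification effects", with baseline HbA1c as a linear covariate. The MMRM in Protocol 7.3.1 adds visit, treatment by visit and baseline HbA1c by visit. Neither model has a term for prior OAD use.

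**The concern.** The eligibility rules create a baseline split that may predict the outcome. One cohort loses a glucose-lowering drug about 12 weeks before baseline. Its insulin is held within 10% or 2 U of the Visit 5 dose from Visit 1 onward (Protocol 3.3.2), and the same limits apply to both cohorts through week 16 unless rescue criteria are met (Protocol 4.2.1). HbA1c still drifting at Visit 5 would therefore be largely uncompensated. It would enter the 16-week change directly, or through rescue, after which SAP 6.6 sets values to missing and carries the last one forward.

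Baseline HbA1c is a level. It cannot tell a stable value from an equal value that is still moving. If cohort carries that information, leaving it out puts explainable variation into the error term and leaves any chance imbalance in cohort share unadjusted. What is at stake is some precision in the two primary comparisons, not their validity.

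**Working it through.** **1. The plan's own figure.** Inputs from Protocol 7.7: difference 0.5, SD 1.0, two-sided alpha 0.05, power 90%.
- The two-sample noncentral t test gives power 0.8999 at 85 per arm and 0.9032 at 86, so 86 reproduces. The normal approximation gives 85.
- 86 / 0.97 = 88.7, rounded up to 89 per arm.
- 0.90 × 0.90 = 0.81 overall power.
- Standard error of a treatment difference: 1.0 × sqrt(2/86) = 0.1525.

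**2. Assumed inputs.** The documents give neither the cohort share nor a cohort difference in outcome. Assumed here: the smaller cohort has share p = 0.2 to 0.5, and the cohort difference in 16-week change, net of the terms already in the model, is d = 0.2 to 0.5 HbA1c points. SD 1.0 is taken as the residual SD without a cohort term.

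**3. Chance imbalance.** 95% limit for the difference in cohort share between two arms of 86: 1.96 × sqrt(2p(1-p)/86).
- p = 0.2: 0.120
- p = 0.5: 0.149

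Multiplied by d, this is the shift in the estimated effect:
- smallest case: 0.120 × 0.2 = 0.024
- largest case: 0.149 × 0.5 = 0.075, which is 15% of the planned 0.5 and 0.075 / 0.1525 = 0.49 of a standard error

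**4. Gain from the term.** Residual variance falls by p(1-p)d².

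| p | d | Variance removed | Residual SD | Power at 86 per arm | n per arm for 90% (normal approximation) |
|---|---|---|---|---|---|
| none | none | 0 | 1.000 | 90.3% | 85 |
| 0.2 | 0.2 | 0.6% | 0.997 | 90.5% | 84 |
| 0.3 | 0.3 | 1.9% | 0.991 | 90.9% | 83 |
| 0.5 | 0.5 | 6.3% | 0.968 | 92.0% | 79 |

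**5. Does the planned standard error already allow for the imbalance?** Yes. Take the largest case. The standard error with the term is 0.1477. The SD of the imbalance is sqrt(2 × 0.25/86) = 0.0762, so the SD of the shift is 0.0762 × 0.5 = 0.0381. Then 0.1477² + 0.0381² = 0.0218 + 0.0015 = 0.0233 = 0.1525². The unadjusted standard error contains the chance shift in full.

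**6. Type I error with cohort omitted.** Simulation with p = 0.3, d = 0.5, 86 per arm and 20,000 runs: 0.0525. The Monte Carlo standard error is sqrt(0.05 × 0.95/20,000) = 0.0015, so this is about 1.6 standard errors from 0.05 and consistent with it.

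**7. Cost of the term.** Analysed patients: 3 × 86 = 258. The ANCOVA with two-level renal function uses 6 parameters (intercept, two for treatment, renal function, insulin type, baseline HbA1c), leaving 252 residual degrees of freedom. The cohort term takes one.

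**8. Cost of a fourth stratum.** Cells go from 2³ = 8 to 2⁴ = 16, and the mean cell size from 267/8 = 33 to 267/16 = 17.

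**The case against.** - **Drift is conjecture.** Protocol 3.2 states what wash-out is for. It does not admit a residual effect, and baseline falls about 12 weeks after the OAD is stopped. This stands: the size of d is unknown, and it must be net of baseline HbA1c, eGFR and insulin type.
- **Regression to the mean.** A reader might infer that qualifying on one value versus two makes the cohorts regress differently. HbA1c is measured again at Visit 5, and baseline is the last value before randomised drug (Protocol 5.1.1, SAP 6.7). Regression from the qualifying values has therefore largely happened before baseline, and this is at most a minor mechanism.
- **The HbA1c stratum.** Its use of different visits might look like a flaw. It follows from insulin-alone patients having no Visit 4 HbA1c; each cohort is stratified on its qualifying value.
- **The plan is coherent and the gain small.** All three stratification factors are represented in the ANCOVA, and any unstratified covariate is left to chance. Both are true, and they limit the weight of the point. Still, few covariates are created by the eligibility rules and already known for every patient.
- **Changing the primary model is not free.** The terms are fixed in the Protocol synopsis, 7.1 and 7.3.1; SAP section 4 declares no changes, and the SAP is marked final. This stands and belongs in the cost.
- **Some SAP text is not visible,** including 6.4 and entries between 7.4.1 and 7.7. A subgroup or sensitivity analysis by prior therapy may exist there. It would not alter the primary model, whose terms are stated in full.

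**Conclusion.** The omission is real and its effect is small. Cohort is a known baseline factor that the stated ANCOVA and MMRM leave out, and it may be prognostic if HbA1c is still drifting after OAD withdrawal. Under the assumed ranges, the term removes 0.6–6.3% of residual variance, raises power from 90.3% to about 90.5–92.0%, and adjusts for a chance shift whose 95% limit is 0.024–0.075 HbA1c points. If d is near zero, the gain is near zero.

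A reader might go further and infer that the primary comparison is biased, that type I error is inflated or that the trial is too small. The documents do not support this. Randomisation balances cohort in expectation, the planned standard error already covers chance imbalance, simulated type I error is consistent with 0.05, and 86 analysed per arm still gives the planned power.

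**What to change.** Before unblinding, add pre-treatment (insulin alone / insulin + 1 OAD) as a fixed classification effect in the primary ANCOVA (Protocol 7.3.1, SAP 7.4.1) and in the MMRM of Protocol 7.3.1, and record it in SAP section 4 as a change from the protocol. The factor needs no new data, because it already decides who is washed out, which visit supplies the HbA1c stratum and which range the violation check applies.

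At minimum, keep the primary model and pre-specify the same ANCOVA with this term as a sensitivity analysis. Protocol 7.3.1 already lets the SAP add sensitivity analyses, so this needs no departure from the protocol.

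Do not add a fourth randomisation stratum: halving the mean cell size is not worth it for a gain this small, and the model term captures most of that gain.

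Cost: one degree of freedom, no change in sample size, a revised SAP and, for the full version, a documented departure from the protocol model. Added after unblinding, the term would be open to challenge as post hoc.

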7.7 DETERMINATION OF SAMPLE SIZE

Based upon previous experience with empagliflozin [[U12-3817-01](#)], it is estimated that the difference of change from baseline in HbA_{1c} after 16 weeks of treatment between empagliflozin (10 mg or 25 mg) and placebo add-on to insulin is 0.5% and that the standard deviation of this difference is 1.0%. The Type I error for each hierarchical testing procedure to evaluate superiority of empagliflozin 10 mg against placebo followed by superiority of empagliflozin 25 mg against placebo, is assumed to be 5% (two-sided), while maintaining the overall probability of type I error at 0.05.

The number of analysed patients should be 86 per treatment arm to have 90% power to test the primary endpoint of each empagliflozin 10 mg and 25 mg, leading to 81% overall power. Assuming that approximately 3% of patients will not be eligible for inclusion into the FAS, 3 additional patients should be randomised per arm. As such sample size will be 89 per arm. Calculations were performed using nQuery Advisor® 7.0.

Meanwhile, the draft version of the revised Japanese guideline “Clinical Evaluation Guidelines for Antihyperglycemic Drugs” [[R15-2907](#)] requires at least 100 patients who are treated for 1 year with oral antihyperglycemic drug. Therefore, assuming a 20 % loss of

Proprietary confidential information © 2016 Boehringer Ingelheim International GmbH or one or more of its affiliated companies

randomised patients during the 52 weeks of treatment, at least 63 patients should be randomised per arm (126 patients from both empagliflozin 10 mg and 25 mg arms).

On the basis of the above, a total of 267 patients (89 per arm) need to be randomised.

8. INFORMED CONSENT, DATA PROTECTION, TRIAL RECORDS

The trial will be carried out in compliance with the protocol, the ethical principles laid down in the Declaration of Helsinki, in accordance with the ICH Harmonized Tripartite Guideline for Good Clinical Practice (GCP) and relevant BI Standard Operating Procedures (SOPs) and the Japanese GCP regulations (Ministry of Health and Welfare Ordinance No. 28, March 27, 1997) and the Japanese GPSP regulations (Ministry of Health, Labour and Welfare Ordinance No. 171, December 20, 2004).

Standard medical care (prophylactic, diagnostic and therapeutic procedures) remains in the responsibility of the treating physician of the patient.

The Investigator will inform the Sponsor immediately of any urgent safety measures taken to protect the trial subjects against any immediate hazard, and also of any serious breaches of the protocol or of ICH GCP and the Japanese GCP regulations (Ministry of Health and Welfare Ordinance No. 28, March 27, 1997).

The rights of the investigator / trial site and of the sponsor with regard to publication of the results of this trial are described in the trial site's contract. As a general rule, no trial results should be published prior to finalisation of the Clinical Trial Report.

The certificate of insurance cover is made available to the Investigator and the patients, and is stored in the ISF (Investigator Site File)."

8.1 TRIAL APPROVAL, PATIENT INFORMATION, AND INFORMED CONSENT

This trial will be initiated only after all required legal documentation has been reviewed and approved by the respective Institutional Review Board (IRB) according to national and international regulations. The same applies for the implementation of changes introduced by amendments.

Prior to patient participation in the trial, written informed consent must be obtained from each patient (or the patient's legally accepted representative) according to ICH / GCP and to the regulatory and legal requirements of the participating country. Each signature must be personally dated by each signatory and the informed consent and any additional patient-information form retained by the Investigator as part of the trial records. A signed copy of the informed consent and any additional patient information must be given to each patient or the patient's legally accepted representative.

The Investigator must give a full explanation to trial patients by using the patient information form, which is prepared avoiding the use of technical terms and expressions. The patient is given sufficient time to consider participation in the trial. The Investigator obtains written consent of the patient's own free will with the informed consent form after confirming that

the patient understands the contents. The Investigator must sign and date the informed consent form.

If a trial collaborator has given a supplementary explanation, the trial collaborator also signs and dates the informed consent.

Re-consenting may become necessary when new relevant information becomes available and should be conducted according to the sponsor's instructions.

8.2 DATA QUALITY ASSURANCE

A quality assurance audit/inspection of this trial may be conducted by the Sponsor, Sponsor's designees, or by IRB or by regulatory authorities. The quality assurance auditor will have access to all medical records, the Investigator's trial-related files and correspondence, and the informed consent documentation of this clinical trial.

8.3 RECORDS

eCRF for individual patients will be provided by the Sponsor via remote data capture. See [Section 4.1.5.2](#) for rules about emergency code breaks. For drug accountability, refer to [Section 4.1.8](#).

8.3.1 Source documents

Source documents provide evidence for the existence of the patient and substantiate the integrity of the data collected. Source documents are filed at the Investigator's site. Data reported on the CRF must be consistent with the source data or the discrepancies must be explained. The Investigator may need to request previous medical records or transfer records, depending on the trial; current medical records must also be available. For eCRFs all data must be derived from source documents.

